## Aims

The purpose of this study is to assess carotid artery MRI plaque characteristics in 100 asymptomatic cancer survivors with history of chest, head and neck radiotherapy (HNXRT) and with subclinical atherosclerosis. Another objective is to analyze plaque changes in the same group after initiation of medical treatment for 18 and 36 months.

The following specific aims (A), research questions (RQ) and hypotheses (H) will be addressed.

A 1: To characterize the plaque constituents including fibrous cap (FC), lipid core and hemorrhage within the carotid plaque by MRI

RQ 1a: What are the predominant plaque constituents?

RQ 1b: Is there a predominance of complex and vulnerable plaque features in the neck arterial vasculature of cancer survivors?

H 1: We hypothesize that there is a predominance of vulnerable plaque in carotid arterial vasculature of HNXRT patients due to the phenomenon of radiation vasculopathy.

A 2: Determine the correlation between plaque inflammation (direct measure by MRI) with serum markers of inflammation through blood tests (hsCRP, LpPLA2, IL-6) and metabolomics

and other tests of cardiac or vascular dysfunction (echocardiography and computerized tomography coronary calcium score studies).

RQ 2: Is there any correlation between the direct and surrogate markers of inflammation?

H 2: We hypothesize that there is a predictable correlation between the direct and surrogate measures of inflammation.

A 3: To assess the longitudinal change in the artery plaque characteristics (inflammation and morphology) with treatment.

RQ 3: Is there a predictable relationship between inflammation (pattern of enhancement-contrast kinetics) and vulnerable features within a plaque?

H 3: We hypothesize that changes in plaque characteristics pre and post treatment would correlate with contrast agent dynamics over time.

A 4: To determine the efficacy of comprehensive treatment (life style modification + statin) versus (life style modification + placebo).

RQ 4: Is one regimen better than the other in cancer survivors with subclinical atherosclerosis?

H 4: We hypothesize that comprehensive treatment (life style modification + statin) would have better inflammation control and favorable plaque modification than life style modification alone as measured by parameters in (A2 & A3).

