#### **Examination Plan Overview:**

All participants will be given IRB approved informed consent. Those who decide to take part and give consent for the study would be enrolled in the research study. We would be taking snap shots with MRI at three data points and monitor treatment effects. Overview of the research study is shown in Fig 2. A baseline MRI will be performed to assess arterial atherosclerotic constituents. Once the initial MRI has been performed, and in the case where subclinical disease is present i.e. elevated blood markers or arterial plaque on MRI. HNXRT cancer survivor patient with abnormal tests will be started on treatment, which includes life style modification and-/or lipid lowering medication. Patients with positive tests would be divided randomly into two groups; one group will receive life style modification + statin therapy and the second group will receive life style modification alone. A repeat MRI and blood tests (2nd study) will be performed at 18 months after initiation of such treatment to assess changes in plaque morphology and enhancement characteristics. MRI findings of baseline and final would be

correlated with surrogate markers of inflammation, Echo and CT findings. A final set of MRI and blood tests will be performed at 36 months after initiation of such treatment to assess changes in plaque morphology and enhancement characteristics. MRI findings of baseline and final would be correlated with surrogate markers of inflammation, Echo and CT findings.

Fig 2. Shows overview of the research study

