#### Treatment and Clinical Follow-Up:

Patients enrolled in the “Accelerated Atherosclerosis in High Risk Population Groups: An Assessment by Magnetic Resonance Imaging” study will be evaluated in the cardiology clinic by [name],

FACC, FSCAI who is the Director of Peripheral Vascular Intervention at Emory University and treats patients with carotid artery disease. All these patients will be randomized based on the last digit of their medical record number. If the last digit will be an even number they will then be given a statin, which they will take and will also be instructed about regular exercise. Patients will be made aware of the side effects of statins and about the procedures to report these side effects. Patients with the last digit being an odd number will ONLY be advised about exercise. All patients will have regular visits and patients on a statin will be followed up and evaluated for any adverse effects of the medication and for compliance at 18 and 36 months by the study preventive cardiologist. The preventive cardiologist or any other physician involved with care of the patient may elect for more frequent follow up as well as modification or discontinuation of the study prescribed therapy if deemed necessary based on his or her best clinical judgment.

These patients will get routine clinical follow-up in the oncology (The Winship Cancer Institute Clinics) and cardiology clinics (Emory Hospital) as part of the ongoing routine clinical care.

Within five weeks of initial MRI evaluation, our recruited research that demonstrate increased blood markers and/or atherosclerosis on MRI would be subjected to life style modification ± medical (statin) therapy. Department of Cardiology would prescribe and monitor statin therapy: Rosuva (20 mg once a day) with target LDL goal < 70; non-HDL goal < 100 and Aspirin (81 mg once a day). The rational for using rosuva 20 mg is because this dosage has already been successfully used in JUPITER Trial (35). The follow-up by Cardiology department would comprise educating the patients on life style modification and also how to monitor and report any adverse drug affects which if expected would be further assessed with laboratory testing with LFT's and CBC. Any patients who suffer clinical side effects of treatment as part of our research would be taken off our study. Patients will continue to follow-up in the survivorship clinic and with the preventative cardiologist as indicated.

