Statistical analysis: The three parameters mentioned above (Ktrans,  $\square_p$ , vessel wall) continuous variables. Before performing the statistical modeling we will check first to see if the distributions of these variables are normal; otherwise, we will use log transformation prior to the modeling of these parameters. We will first compute the mean, median, and standard deviation at each time point for these parameters. We will plot these data by patient over the 3 time points to examine the longitudinal profiles. We will use the linear mixed effects model (random coefficient model with random intercept and slope) with these parameters serving as dependent variables. The independent variables will be the time indicator and other potential confounders that we may need to control (e.g. age, gender, race, and body mass index). The interest in this model is the coefficient associated with the time indicator, which allows us to obtain the adjusted population mean estimate of these parameters at each of these time points. Since we have the best linear unbiased prediction estimates of the random intercepts and slopes for each subject,

we will be able to examine individual subject profiles and assess the temporal trend for each subject. Thus this random coefficient linear mixed effects model will allow us to obtain the overall adjusted mean estimate ( $K_{trans}$ ),

for each of the individual subjects, overall across all above mentioned time points, and at each of the time points.

To assess the association between the vessel wall area, and  $K_{trans}$  and

linear mixed effects models (random coefficient models) to obtain the estimates of fixed effects.

We will carry out 2 analyses in these models, we will use vessel wall area as the dependent variable and  $K_{trans}$  and

potential confounders if necessary. The slope estimate from these models is interpreted as a measure of adjusted association between the changes in plaque size and morphology, and DCE-MRI dynamic enhancement parameters.

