#### Expected results:

We anticipate that the  $K_{trans}$  and

the size of the plaques (vessel wall area) will change in a favorable way over the time course of the study due to institution of treatment (medicines and life style modification). We anticipate that changes in the vessel wall (plaque and vessel wall remodeling) as measured by high-resolution MRI will change in a way that is predicted by the change in the DCE-MRI inflammation parameters but that changes in the DCE-MRI inflammation parameters will precede those of the morphological changes. We expect this because previous studies have shown changes in inflammatory cell content occur within three months of the initiation of statin therapy, whereas changes in plaque morphology as measured by high-resolution anatomical

MRI occur at approximately twelve to eighteen months following the initiation of statin therapy (19, 41, 42).

A # 2: To investigate the relation between direct measures of plaque inflammation (MRI) and indirect measures of inflammation (blood serum markers of inflammation, Echocardiographic and CT studies) as therapy progresses.

Rationale: DCE-MRI studies have shown a correlation between the number of macrophages and amount of neovasculature and the patterns of dynamic contrast enhancement (42, 43). Our hypothesis is that over a longer period of time (36 months); there would be a correlation between these two (direct and indirect measures of inflammation).

Data analysis: The DCE-MRI dynamic enhancement parameters (Ktrans and  $\square_p$ ) will be determined as described in section SA # 3 above. Samples will be drawn for serum markers of inflammation (hsCRP, LpPLA2, IL-6). Relationship if any between the inflammation within the plaque and serum markers will be observed.

Expected results: We expect a predictable correlation between the inflammatory markers in the blood and inflammation present within the vessel wall/plaque seen on the initial and post treatment sampling; this expectation is based on prior literature (19, 22, 46, 47).

We will carry out the modeling using SAS/STAT procedure MIXED.

A # 4: To determine the efficacy of comprehensive treatment (life style modification + statin) versus life style modification alone.

Rationale: The effects and efficacy of various combinations of treatment have not been studied in the context of radiation vasculopathy and accelerated atherosclerosis.

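### As written, the statin arm also gets daily aspirin and the control arm does not, so Aim 4 can estimate only a joint statin-plus-aspirin effect although it names the statin as the sole difference

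*Combined protocol and SAP*

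**What the plan says.** The hypothesis for Aim 4 (Aims, H 4) is that "comprehensive treatment (life style modification + statin) would have better inflammation control and favorable plaque modification than life style modification alone". The Examination Plan Overview describes the arms in the same way: "one group will receive life style modification + statin therapy and the second group will receive life style modification alone". The A # 4 text under Specific Aims repeats it: "comprehensive treatment (life style modification + statin) versus life style modification alone". The statement of A 4 in the Aims section differs in one respect, because it names a placebo comparator. None of these statements mentions aspirin.

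The Treatment and Clinical Follow-Up section assigns patients by the last digit of the medical record number. Even-digit patients get a statin and exercise instruction. For the others, "Patients with the last digit being an odd number will ONLY be advised about exercise". Later in the section, the drug regimen under the Department of Cardiology is set out as follows: "statin therapy: Rosuva (20 mg once a day) with target LDL goal < 70; non-HDL goal < 100 and Aspirin (81 mg once a day". This is the only mention of aspirin in the readable text.

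The dose justification that follows covers one of the two drugs: "The rational for using rosuva 20 mg is because this dosage has already been successfully used". The compliance check is directed at one arm: "patients on a statin will be followed up and evaluated for any adverse effects of the medication and for compliance". The mixed model under Specific Aims (A # 3, statistical analysis), which A # 4 reuses, allows for "potential confounders that we may need to control (e.g. age, gender, race, and body mass index".

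**The concern.** Aim 4 will be read as what a statin adds to lifestyle modification in irradiated cancer survivors. If aspirin starts with the statin in one arm and is not offered in the other, any difference between arms in Ktrans, vessel wall area or the serum markers is the combined effect of two drugs. H 4 would credit all of it to the statin.

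The A # 4 text says that patients act as their own controls. That does not separate the drugs, because both start together. No later analysis of the assigned groups can separate them either.

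**Working it through.** **1. The plan's own figure.** The Sample Size section powers Aims 2 and 3 only, so there is no Aim 4 figure to reproduce. The 92 subjects come from Aim 3: an ANOVA with effect size 0.28, three measurements and alpha 0.05. A one-way ANOVA with k = 3, f = 0.28 and n = 92 per time point, treated as independent groups, gives power 0.990, which matches the plan. The figure is used here only as the source of 92 / 2 = 46 completers per arm.

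**2. The arms side by side.**

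| Source | Statin arm | Control arm |
|---|---|---|
| Aims, A 4 | lifestyle + statin | lifestyle + placebo |
| Aims, H 4; Examination Plan Overview; A # 4 | lifestyle + statin | lifestyle alone |
| Treatment and Clinical Follow-Up, plain reading | lifestyle + rosuvastatin 20 mg + aspirin 81 mg | lifestyle, no study drug |

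The last row reads the section as intending the same lifestyle programme in both arms, with only the medical therapy varying.

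**3. What can be estimated.** Let S be assigned statin and A assigned aspirin, with mean outcome b0 + bS·S + bA·A. In the last row A = S for every patient, so:

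- the arm difference is bS + bA (plus any interaction);
- the design matrix (intercept, S, A; 46 v 46) has 3 columns and rank 2, and the two drug columns have correlation 1;
- 0 patients are assigned to statin without aspirin, and 0 to aspirin without statin.

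Only the sum is estimable, and a larger sample would not change that. This step needs no assumption beyond the plain reading of the text.

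**4. Unassigned aspirin in controls.** If a proportion p of control patients take aspirin through routine care, the arm difference becomes bS + bA(1 − p). That use is not randomised. The readable text does not provide for recording it, so p would be unknown.

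**5. Illustration only.** The documents give no aspirin effect. Assume 0 to 0.3 SD, an equal split of 92, and a two-sample t test in place of the planned mixed model.

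- SE of the difference = √(2/46) = 0.2085 SD; critical t on 90 df = 1.987; smallest significant difference = 1.987 × 0.2085 = 0.414 SD.
- Aspirin's share of that difference: 0.1/0.414 = 24%, 0.2/0.414 = 48%, 0.3/0.414 = 72%.

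Chance of a significant arm difference if the statin does nothing (noncentral t, two-sided 5%):

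| Assumed aspirin effect | No control aspirin | Half of controls on aspirin (p = 0.5) |
|---|---|---|
| 0 | 5.0% | 5.0% |
| 0.1 SD | 7.6% | 5.6% |
| 0.2 SD | 15.8% | 7.6% |
| 0.3 SD | 29.6% | 11.0% |

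**The case against.** **Aspirin may have been meant for everyone.** The whole point rests on one loosely written sentence, and the Examination Plan Overview describes the drug component only as lipid-lowering. A reader might infer that the plan has settled on aspirin for the statin arm alone. One sentence does not carry that much certainty. It is the plain reading, because aspirin sits in the list that defines the statin regimen and controls get exercise advice only. If aspirin was for all, then that restriction, and the description of the control arm as lifestyle alone, are wrong. Both readings call for a correction.

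**Aim 4 may compare regimens.** RQ 4 asks which regimen is better, and the A # 4 data analysis compares regimens. On that view the joint effect is a valid target and the label is merely incomplete. This stands in part, and it is why renaming is an adequate remedy. But the plan defines comprehensive treatment in brackets as lifestyle plus statin, and H 4 follows that definition.

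**Aspirin may be monitored after all.** A reader might infer that it goes unmonitored. The text does not support that. If the statin regimen includes aspirin, the instruction to prescribe and monitor it covers aspirin too. The section also provides generally for reporting adverse drug effects, with liver tests and blood counts. What remains is the lack of any record of aspirin use in control patients. The covariate list is given only as examples, so leaving aspirin out of it shows little. Assigned aspirin could not be adjusted for in any case.

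**Other problems are larger.** Allocation by record number and the placebo that appears only in A 4 also threaten Aim 4. They are separate. Concealed allocation with a matching statin placebo would still leave aspirin in one arm.

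**Conclusion.** The point holds as an inconsistency that needs correcting. On the plain reading of Treatment and Clinical Follow-Up, assigned statin and assigned aspirin coincide completely, so Aim 4 yields a joint effect that H 4 would attribute to the statin. The size that comes from the documents is the zero overlap: no patient is assigned one drug without the other.

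A reader might take the percentages in the illustration as a false-positive rate of up to 29.6%. The documents do not support that. The aspirin effect is assumed, Aim 4 has no sample size calculation, and for a comparison of regimens those results would be true effects. The figures should not bear on how serious the point is.

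Aim 4 is not one of the aims that set the sample size, so this should be fixed but does not undermine the whole study. Two limits apply: the overview figure (Fig 2) is not shown, and the documents do not say whether patients are already enrolled.

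**What to change.** - **Preferred.** In Treatment and Clinical Follow-Up, take aspirin out of the regimen assigned to one arm and state a single rule for both: aspirin by clinical indication. Reword the odd-digit sentence to say that these patients get the same lifestyle programme and the same aspirin rule, without the statin.
- **If aspirin stays in the statin arm only, or patients are already enrolled under that regimen.** Rename Aim 4, RQ 4 and H 4 as lifestyle + statin + aspirin versus lifestyle alone, and claim no statin-specific effect.
- **In either case.** Record aspirin and statin use in both arms at baseline, 18 and 36 months, and tabulate it with the Aim 4 result.

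The cost is one or two protocol sentences, or a relabelled aim, plus a short drug record at visits that already take place. With open allocation, physicians may still prescribe aspirin differently by arm, so some imbalance can remain, but it would be visible.

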**Adverse Event Reporting:**

We do not expect any serious physical adverse events from this research study. Participating in this study involves very few/minimal risks. Study staff will work with patients to minimize any stress or discomfort with the study procedures. The study involves a blood draw, which may cause slight bruising or pain at the site where the blood is drawn. In addition, bleeding, dizziness, fainting or feeling lightheaded, nausea, hematoma or infection may occur because of drawing your blood. The blood will be drawn from expert/trained staff so this will be less likely to happen.

The Computed Tomography (CT) for coronary artery calcification (CAC) and Echocardiogram are both non-invasive procedures. CT exams are generally painless, fast and easy. The risks associated with CAC screening are small (48). The echocardiogram is very safe, painless and uses ultrasound waves, for which there are no known risks.

We do not expect any serious physical adverse events from MRI examinations. Due to recent concerns related to the use of gadolinium-based contrast agents in patients with renal dysfunction and risk of nephrogenic systemic fibrosis (NSF), serum creatinine levels will be measured from blood drawn before each MRI examination (49). Patients with normal renal function values will be administered contrast and this approach virtually eliminates any possibility of NSF.

Statin treatment might cause some side effects in few individuals which would be closely monitored by symptoms and followed by blood tests; if any side effects occur, the medication would be immediately stopped; patients would be taken off the study protocol and they would continue their routine follow up in The Survivorship and Cardiology clinics.

Subjects will be provided with telephone numbers of the PI, co-investigators and the Emory University IRB. Any adverse events will be appropriately documented and reported through the Department of Radiology Safety Committee.

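### The only dated checks of adverse effects and compliance are for statin patients, and nothing records statin or aspirin use in the lifestyle-only arm

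*Combined protocol and SAP*

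**What the plan says.** Under Treatment and Clinical Follow-Up, allocation follows the last digit of the medical record number. Even-digit patients receive a statin and exercise instruction. For the others: "Patients with the last digit being an odd number will ONLY be advised about exercise".

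On follow-up, the section says "All patients will have regular visits", without interval or content, and continues in the same sentence that "patients on a statin will be followed up and evaluated for any adverse effects" of the drug, and for compliance, at 18 and 36 months. The preventive cardiologist or any other treating physician "may elect for more frequent follow up as well as modification or discontinuation of the study prescribed therapy". A later paragraph repeats that randomized therapy may be changed by any physician involved in care, at a scheduled visit or at any other time. Liver function tests and a blood count are tied to an adverse drug effect being expected (apparently meaning suspected).

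Under Adverse Event Reporting: "Statin treatment might cause some side effects in few individuals which would be closely monitored by symptoms and followed by blood tests". If side effects occur, the drug is stopped and "patients would be taken off the study protocol". The same section ends with a general commitment, not limited to one arm, to document adverse events and report them through a departmental safety committee. It gives no form, timing or method of asking.

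**The concern.** Aim 4 compares lifestyle modification plus statin with lifestyle modification alone. Two kinds of information are needed to interpret that comparison, and the plan arranges for both mainly in one arm.

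The first is harms. If one arm is asked about symptoms at set times and the other is not, a complaint that is equally common in both will appear more often in the arm that is asked. As the treatment section describes delivery, controls take no study tablet, so a non-specific complaint is also more readily blamed on treatment in the statin arm, where it can lead to removal from the study.

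The second is treatment actually received. Participants have subclinical cardiovascular disease and routine cardiology follow-up, and their physicians are free to change therapy. Some controls may take a statin. If nobody records it, a small difference between arms could mean a weak effect or a diluted one, and the data could not separate the two.

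**Working it through.** The plan gives no figure for harms, compliance or control-arm statin use, so there is nothing to reproduce. The main check is textual; the arithmetic only gives scale.

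**Text, side by side**

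| Item | Statin arm | Lifestyle-only arm |
|---|---|---|
| Regular visits, content unstated | Yes | Yes |
| Dated adverse-effect evaluation | 18 and 36 months | None stated |
| Dated compliance evaluation | 18 and 36 months | None stated |
| General documentation of adverse events | Yes | Yes |
| Record of non-study statin or aspirin use | None stated | None stated |
| Physician may change therapy at any point | Yes | Yes |

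Aspirin matters because the treatment section lists it together with the statin. The eligibility criteria do not exclude people already taking a statin, and the baseline variables listed under Health Evaluation of Patients do not include current cardiovascular medication.

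**Scale 1: unequal capture of harms**

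Assume the same true event rate p in both arms, full capture on statin, and a captured fraction q in controls. The apparent risk ratio is p / (p × q) = 1/q.

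- q = 0.75: 1/0.75 = 1.33. With p = 10%, 10% against 7.5% would be recorded.
- q = 0.50: 1/0.50 = 2.0. With p = 10%, 10% against 5% would be recorded.

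Both p and q are assumptions.

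**Scale 2: dilution of the Aim 4 comparison**

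Inputs: 100 recruited (Sample Size). Assumed: an even split of 50 per arm, two-sided alpha 0.05, and a continuous outcome in SD units. The effect is set so that power is 80% when no control takes a statin. The plan bases its power on Aims 2 and 3 and states none for Aim 4, so 80% is a convention, not a plan figure.

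- Effect with 80% power: (1.960 + 0.842) × √(2/50) = 2.802 × 0.2 = 0.56 SD.
- If a share c of controls takes a statin with full effect, the mean difference shrinks to 0.56 × (1 − c). Power is Φ(2.802 × (1 − c) − 1.960).

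| c | 2.802 × (1 − c) − 1.960 | Power |
|---|---|---|
| 0 | 0.842 | 80% |
| 0.10 | 0.561 | 71% |
| 0.20 | 0.281 | 61% |
| 0.30 | 0.001 | 50% |

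With 46 per arm (half of the 92 in Sample Size) the starting effect is 0.58 SD and the power column is unchanged, because the effect is again set to give 80%.

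**Monitoring wording**

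Adverse Event Reporting promises that side effects "which would be closely monitored by symptoms and followed by blood tests". In the treatment section the only dated evaluations are at 18 and 36 months; anything more is discretionary or has no stated interval. A site could not tell from the two sections together what close monitoring requires.

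**The case against.** The strongest defence has four parts.

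1. The dated evaluation concerns adverse effects of the medication and compliance with it. Controls have no study drug, so there is nothing of that kind to evaluate. This explains the wording but does not remove the need for a common symptom question and a record of what controls take.
2. Adverse events are to be documented without limit to one arm, all patients have regular visits, and routine oncology and cardiology follow-up continues. This stands. A reader might infer that control-arm events would not be counted at all; the documents do not support that. But passive documentation is not equal to scheduled questioning. The flow sheets in the HeartWise programme track exercise, not statin use.
3. A reader might also infer that removals for side effects can occur in one arm only. The removal rule in the treatment section refers to side effects of treatment, and Examination Plan Overview counts lifestyle modification as treatment. The rule can therefore reach both arms; the version under Adverse Event Reporting is the statin-specific one. More removals on statin are likely, not certain.
4. Hypothesis 4 defines benefit by inflammation and plaque measures, and no between-arm comparison of harms is specified. This also stands: unequal questioning about harms does not by itself bias the answer to RQ 4. Unrecorded control-arm statin use and unequal loss do bear on it.

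On monitoring, it is tempting to say that the two sections contradict each other. They do not quite. Close monitoring has no stated interval, the treatment section allows extra visits and patient reporting, and the blood-test wording in both places can be read as triggered by symptoms.

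**Conclusion.** The concern holds in a limited form. Scheduled questioning about adverse effects and compliance is one-sided, and no section plans to record statin or aspirin use in the lifestyle-only arm. Any by-arm account of harms would carry ascertainment bias: an apparent risk ratio of 1.33 to 2.0 with no true difference, if controls' events are captured 75% to 50% as completely (assumed). Dilution of the Aim 4 comparison could not be measured. If 10% to 30% of controls took a statin, a design with 80% power would fall to about 71% to 50%, assuming 50 per arm and full statin effect in those controls. These are illustrations; the textual gap does not depend on them.

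The monitoring statements are in tension rather than contradiction and need reconciling.

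**What to change.** At the 18- and 36-month contacts already planned for MRI and blood tests, put the same adverse-effect questions and the same statin and aspirin-use questions to both arms, on one form, and report the answers by arm. Suggested wording: *At the 18- and 36-month contacts, adverse effects and any use of statin or aspirin, whether or not prescribed by the study, will be recorded on the same form in both arms and summarised by allocated arm.*

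Separately, reconcile Treatment and Clinical Follow-Up with Adverse Event Reporting on when adverse effects and laboratory tests are assessed. No schedule is proposed here; that is for the clinical investigators.

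The cost is a short extra form for controls at existing contacts, one by-arm table and a wording change. The questions themselves change no one's treatment. Information not collected during follow-up may not be reliably recoverable later.
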